FLS tasks. In addition to above recruitment methods we will consider the use of social media and direct emails to increase trainee recruitment for the study. Trainees will be able to volunteer their help by replying to a secure email address. Those trainees who respond and meet the inclusion criteria will subsequently be invited to attend a study day to perform four FLS tasks with a choice of 6 days across 3 possible weekends. On the day, they will be asked to fill out another short questionnaire to gather some demographic information and account for potential confounding variables. Personal details from these questionnaires will be separated and a study number will be randomly allocated to both parts of questionnaires and this number will be written on the trainee's badge which will be used for filling out the task evaluation sheets. A single sheet of paper will allow us to recognise the study number against the relevant trainee in case we need to contact them at some point. This form will be securely stored in a locked cabinet in an NHS locked office accessible only to the research team. A sub selection of trainees will be randomly chosen to have electromyography (EMG) and electroencephalography (EEG) monitoring whilst performing the tasks.

The email accompanying the questionnaires will contain a brief introduction to the study, a participant information sheet and consent form as attachments. Trainees will be able to self select if they meet the inclusion criteria and volunteer their participation for the FLS tasks. At this point they will be asked to provide us with contact details so that we can contact them to verify their suitability for the study prior to attendance and go through the different dates for them to choose a convenient slot.

Study Population

Trainees (Inclusion Criteria):

We will recruit 20 trainees from GS and 20 trainees from O&G in the north west deanery in the following proportions:

Obstetrics and Gynaecology (O&G)	General Surgery (GS)
ST3/ST4/ST5* (n=10)	ST3/ST4/ST5* (n=10)
ST6/ST7 (n=10)**	ST7/ST8 (n=10)

* ST5 trainees with limited experience at this grade and are functionally at grade ST4. This include ST5 trainees who have less than 3 months of experience at this grade or its equivalent for part time trainees.

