Personal details from these questionnaires will be separated and a study number will be allocated to both parts of questionnaires. The same study number will be written on the trainee's badge as this number will be

used for filling out the evaluation sheets. A single sheet of paper will allow us to recognise the study number against relevant trainee in case we need to contact them at a later point. This form will be securely stored in a locked cabinet in an NHS locked office accessible only to the research team.

There are four FLS tasks and they are carried out using validated training models called LASTT (Laparoscopic Skills Training and Testing method) and SUTT-1 (Suturing and knot tying Training and Testing method). LASTT is a wooden model and SUTT-1 is a foam sponge.

A sub selection of trainees will be randomly chosen on the day (with their consent) to have EMG and EEG monitoring whilst performing these tasks.

A summary of the tasks is given below in table 1 below followed by a more detailed explanation later in this section.

Table 1: Summary of FLS tasks.

Task	Task Aim	Ideal time for completion	Data to be recorded*
1	Camera navigation to find 14 targets – repeated 3 times	Ideal time for completion of task 1 is 2 minutes and 30 seconds. For trainees unable to achieve the ideal target time can continue up to a maximum of 5 minutes.	Time taken (min/sec) to find 14 targets if within 5 minutes. If trainee exceeds 5 minutes then we will record last target found. Penalty- subtracting 1 target from the total found targets if ideal time of 2:30 is exceeded.
2	Transfer 6 objects (repeated 3 times)	Ideal time for completion of task 2 is 3 minutes	Time taken (min/sec) No of objects dropped
3	Position 6 objects (repeated 3 times)	Ideal time for completion of task 3 is 3 minutes	Time taken (min/sec) No of objects dropped
4	Perform 4 interrupted sutures and 4 knots. (done once only)	Maximum time allowed is 15 minutes	Time taken (min/sec) Quality of the sutures and knots***

***The quality of the sutures and knots will be assessed after the completion of the task by 2 independent assessors using validated tools.¹⁰

EMG and EEG readings will be recorded on a subsection of trainees whilst performing the laparoscopic tasks - 4 GS trainees at grade ST3/ST4/ST5, 4 trainees at ST7/8 from GS and, likewise, 4 O&G trainees at ST3/ST4/ST5 and 4 trainees at ST6/7 from O&G.

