The task will be set up by the facilitator and will give the trainee standardised instructions and a short demo video on how to perform this task (**Appendix 7**). The task begins when the trainee inserts the camera to find the character on the first target (e.g. **1**), zoom in and identify the small size character (e.g. **a**) located next to it. Before they can proceed to the next target, the facilitator needs to confirm that they are happy with the identification and placement of the small character by saying "next". Trainee can demonstrate this by placing the target in the circle on the screen and reading it out. Trainee can then navigate the camera to find the next target on the LASTT model which in the above example will be large character '**A**', then zoom in to find the small character next to it, put the small character in the circle on the screen and read it out. They can then move on when indicated by faculty as ok to do so. Trainee can then continue until they find the 14th target "**N end**" which completes the task. Please see figure 1 for an example. The facilitator will record the trainee's study number (badge number) and time taken to identify 14 targets. A time of 2 minutes and 30 seconds is considered as ideal for completion of this task. If trainee exceed this time then it will incur a penalty. For every

30 seconds they exceed beyond 2 minutes and 30 seconds, 1 target will be subtracted from the total number of targets they have found. The penalty column does not need to be completed at the time of assessment and can be worked out retrospectively. Furthermore maximum time allowed for this task is 5 minutes and if all 14 targets have not been identified within 5 minutes then the trainee is encouraged to move on to the second sequence of this task, i.e. round 2. The assessor will be required to record the last target found on the evaluation sheet if 5 minutes limit is reached and the task is still incomplete. The rationale for the 5 minute cap is to minimise fatigue. This task will be repeated 3 times and above data will be recorded on the evaluation sheet (**Appendix 8**). To avoid memory effect the sequence of targets will be changed each round so that there are 3 different sequences to find. The same 3 sequences will be used for all trainees throughout the testing phase (**please see the end of appendix 7**).

Task 2 - Hand eye co-ordination (HEC)

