- Task 1 is ideally completed in 2 minutes and 30 seconds, however trainees will not be confined to this time and will be allowed to continue until all 14 targets have been identified or reached 5 minutes. The rationale for putting a time limit of 5 minutes per round is to avoid fatigue. We will record the time taken (in minutes and seconds) to locate the 14 targets and will average this across 3 rounds. If the task is incomplete by 5 minutes, we will record the last found target (small character). Those trainees who are able to complete the task but have taken longer than 2 minutes and 30 seconds will incur a penalty. For every 30 seconds exceeded beyond 2 minutes and 30 seconds we will subtract 1 target from the total number of targets they have found.
- For tasks 2-3, we will record the time taken in minutes and seconds to complete the tasks and use an average of this across 3 rounds. If the tasks are not completed within time (i.e. 3 minutes) then we will record the number of objects handled within 3 minutes and take an average of this across 3 rounds. Where participant shows mixed/inconsistent performance (i.e. completes the task once in time (i.e. 3 minutes) but not on the other two runs then we will use the average number of handled objects over 3 runs and note the performance as mixed/inconsistent. If an object is dropped whilst being handled, the number of drops will be recorded as this indicates inefficient performance.
- For task 4 the number of sutures, correct knots and extent of trauma will be recorded on the evaluation sheet and maximum time allowed will be 15 minutes.

Secondary outcome measures:

- EMG and EEG signal analysis.
- Qualitative measures such as consultant's perception of trainee's laparoscopic ability and the abilities they regard as important at CCT using a likert scale of 1-5.

Regulatory issues

Consent

The research team responsible for conducting the study are trained medical practitioners and are able to assess capacity and take informed consent.

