Grasp the plastic head of the pin with Johan forceps using your non-dominant hand and lift the pin up.

Whilst elevated, pass the pin to the dominant hand by grasping the metal part of the pin with a Maryland grasper.

Place the pin (head or tail) in the corresponding coloured disc and repeat for all colours. Once the pin is positioned in the disc of the same colour, you may move on to the next coloured push pin. It is not necessary to position the entire length of the pushpin in the respective circle. You may use both hands to stop the pin from falling out.

You are only required to place 6 pins in their respective circles, i.e. one of each colour. If the pin is dropped, use the second pin of the same colour or you may re-grasp the fallen pin, as long as you can find the pin within the endoscopic boundaries.

This task will be repeated 3 times with 3 different colour sequences.

Exercise 4: Suturing and knot tying

The aim of this task is to perform 4 interrupted stitches using correct needle handling and intra-corporeal knot tying techniques.

Perform 4 interrupted sutures by taking a needle bite through the black dots in a horizontal plane. Please use the first 4 rows for your sutures and leave the 5th row.

Pass the suture by entering and exiting precisely within the black dots.

Perform an intra-corporeal knot with 3 throws. Ensure that the knot is secure.

Cut the excess suture using laparoscopic scissors leaving behind a tail of approx. 1-2cm.

[figure not shown]
The link to the video demonstration for tasks 1-3 is:

<https://europeanacademy.org/training-tools/lastt/>

[figure not shown]
The link to suturing demonstration video is:

<https://www.youtube.com/watch?v=2qCBvbWBJ64>

[figure not shown]
Below are the 3 different sequences to be used in task 1.

Sequence 1

Sequence 2

Sequence 3

The following are 3 different colour sequences to be used in task 2 and 3.

Colour sequence 1 for tasks 2 and 3

Colour sequence 2 for tasks 2 and 3

Colour sequence 3 for tasks 2 and 3.

Appendix 8

Task evaluation sheets for laparoscopic tasks

Please indicate the time as you read it on the stopwatch in MM:SS:HH

Task 1: Laparoscopic Camera Navigation (LCN)

Runs	Time required for identifying all 14 targets. (If within or up to 5 minutes taken).	If 5 minutes are exceeded, record the last found target (small character).	Penalties. To be filled after study tasks are completed.
1	: :		
2	: :		
3	: :		

Task 2: Hand- Eye Co-ordination (HEC)

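### Task 1 has two primary scores with no choice between them, and the penalised count is a coarse copy of time that cannot separate trainees finishing within 2:30

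*Protocol*

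**What the plan says.** Under Outcome measures, the primary outcome bullet for Task 1 sets out two quantities.

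- **Time:** "We will record the time taken (in minutes and seconds) to locate the 14 targets and will average this across 3 rounds".
- **A penalised count:** "Those trainees who are able to complete the task but have taken longer than 2 minutes and 30 seconds will incur a penalty", with the rate given as "For every 30 seconds exceeded beyond 2 minutes and 30 seconds we will subtract 1 target from the total number of targets".

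The bullet does not say which of the two is compared between general surgery and O&G.

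The Task 1 description allows the penalty to be worked out after the session. The Appendix 8 sheet has a matching column ("Penalties. To be filled after study tasks are completed") beside a stopwatch time read to hundredths. That time is entered only for rounds finished by 5:00. For the others the sheet holds the last target found.

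Two details of the penalty differ between sections:

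- **Rate:** Table 1 describes a single deduction ("Penalty- subtracting 1 target from the total found targets if ideal time of 2:30 is exceeded"), while the Task 1 description and Outcome measures give one target per 30 seconds.
- **Who incurs it:** the Task 1 description applies it to anyone over 2:30 ("If trainee exceed this time then it will incur a penalty"), while Outcome measures ties it to those who complete the task.

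On sample size: "We will recruit 20 trainees from GS and 20 trainees from O&G in the north west deanery", split into 10 per grade band.

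**The concern.** For a round in which all 14 targets are found, the penalised count is calculated entirely from the recorded time. It adds no information, and it discards some by rounding to 30-second steps and stopping at 14. The ceiling lies at the time the protocol itself calls ideal, which is where the more skilled trainees would be expected to fall if the task works as intended.

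Two things are at stake. First, with two primary quantities from one measurement, the same data can give two different Task 1 answers. Second, if the count is the one compared, a real difference between two fast groups could appear as no difference. Groups of 20, or 10 within a grade band, leave little power to spare.

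**Working it through.** The protocol states no power, significance level, effect size or expected times, so there is no figure of its own to reproduce. The scoring result in step 1 needs no assumptions. The power figures in step 2 do.

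**Step 1. Score of a completed round.** With t the time in seconds (t ≤ 300), the count is 14 − k. Here k is the number of 30-second blocks in max(t − 150, 0), taken as whole blocks (rounded down) or as any started block (rounded up). The text does not say which.

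| Time (s) | Whole blocks | Started blocks | Table 1 single deduction |
|---|---|---|---|
| 90 | 14 | 14 | 14 |
| 150 | 14 | 14 | 14 |
| 179 | 14 | 13 | 13 |
| 180 | 13 | 13 | 13 |
| 210 | 12 | 12 | 13 |
| 240 | 11 | 11 | 13 |
| 270 | 10 | 10 | 13 |
| 300 | 9 | 9 | 13 |

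Six values are possible, 9 to 14. All rounds of 2:30 or less tie at 14, and so do rounds up to 2:59 if only whole blocks count.

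If only completers are penalised, the order can also invert. A completer at 4:45 (285 s) has 135/30 = 4.5 blocks and scores 10 or 9. A non-completer who found 12 or 13 targets keeps 12 or 13.

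**Step 2. Power if the count is the score compared.** Assumptions:

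- log-normal times, with 20% between-trainee and 20% within-trainee variation;
- slower median 1.25 times the faster;
- three rounds averaged per trainee, two-sided t-test at 5%;
- targets found by non-completers proportional to 300/t;
- time capped at 300 s for the comparison.

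The share of rounds within 2:30 in a group with median m is Φ(ln(150/m)/√(0.2² + 0.2²)). For medians 90 and 112.5 s this is Φ(1.81) = 0.96 and Φ(1.02) = 0.85, so about 90% overall lie at the ceiling.

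Power for 20 against 20, whole blocks, everyone over 2:30 penalised:

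| Medians (s) | Capped time | Penalised count |
|---|---|---|
| 90 / 112.5 | about 83% | 7–8% |
| 110 / 137.5 | 84% | 39–42% |
| 180 / 225 | 84% | 79% |
| 200 / 250 | 84% | 82% |
| 240 / 300 | 80% | 82% |
| 300 / 375 | 69–71% | 83–84% |

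Ranges are differences between simulation runs. Counting started blocks softens the loss among fast groups (38% at the 90 s median). If only completers are penalised, time keeps its lead at 240/300 s (80% against 67–68% with whole blocks, 44% with started blocks), and the two are about equal at 300/375 s.

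**Step 3. Sensitivity.** With 25% between-trainee variation, time against count is 70% against 11% at a 90 s median, 70% against 56% at 150 s, 69% against 67% at 210 s and 66% against 68% at 240 s. At 240 s, 37% of rounds pass 5:00. For 10 against 10, with that variation and a ratio of 1.35, it is 63% against 5% at 90 s and 58% against 62% at 240 s. The pattern is the same.

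**Step 4. One ordered score.** Ranking completed rounds by time, and placing unfinished rounds below them in order of targets found, gave 81–84% power at every median from 90 to 300 s in the step 2 model. That is at or within about 2 points of the best alternative throughout.

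**The case against.** A reader might infer that the penalty replaces time, or that it costs power in general. The documents support neither.

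- **Time is kept in the same bullet.** Nothing says the count will be the score tested, and a statistical analysis plan that is not shown could settle this. This stands as far as power goes: the loss is conditional. It does not remove the point, because the protocol itself writes both quantities and the deduction into the primary outcome.
- **The loss depends on times the protocol does not give.** This stands. The 5:00 cap and the non-completion rule show that slow rounds are foreseen. When many rounds pass 5:00 and non-completers are penalised too, the count does better than capped time.
- **Using time alone would be worse for slow groups.** This stands. No completion time exists for rounds past 5:00. Averaging time over completed rounds only gives 46% power at 240/300 s and 17% at 300/375 s, against 82% and 84% for the count with everyone penalised. The count does put finishers and non-finishers on one scale, so the remedy must do so too.
- **Performance against an ideal time is a legitimate thing to measure.** True, but the proportion of rounds within 2:30 shows it directly, without a stepped score in the primary outcome.

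**Conclusion.** The point holds in a conditional form. Two things are certain from the text alone: the primary outcome names two Task 1 quantities without choosing one, and for completed rounds the count is a six-value copy of the recorded time that ties every round of 2:30 or less.

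The effect on power depends on how fast trainees are. It is severe when most rounds fall within 2:30 (about 83% down to 7–8% at a 90 s median) and substantial at 110 s. It is only about 2 to 5 points at 180–200 s if everyone over 2:30 is penalised, and reversed when many rounds pass 5:00 and non-completers are penalised. That final-years trainees will mostly finish within 2:30 is plausible but not documented.

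All power figures rest on the assumed distribution, variation and ratio. They show direction and rough size, not what this study will see. The change is worth making because an ordering built from data already collected does well across the whole range tested.

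**What to change.** In Outcome measures, with matching edits in Table 1 and the Task 1 description, make one ordered Task 1 score primary:

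- Rank completed rounds by recorded time.
- Place rounds unfinished at 5:00 below all completed rounds, ordered by number of targets found (read from the last target and the fixed sequence). Alternatively, analyse time as censored at 5:00.
- Remove the penalty deduction from the primary outcome, and report the proportion of rounds within 2:30 descriptively.
- If the penalty is kept in any form, reconcile its rate (Table 1 against the Task 1 description and Outcome measures) and who incurs it (Task 1 description against Outcome measures). State also whether a started 30-second block counts.

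Cost: rewording and one explicit rule for unfinished rounds, with no new data. A rank-based or censored summary is slightly less simple to present than a mean, so mean times can be tabulated beside it where most rounds are completed. The penalised score becomes descriptive only.

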Runs	Time required for inserting 6 cylinders OR 3 minutes	No of cylinders placed in 3 minutes	No of dropped objects
1	: :		
2	: :		
3	: :		

Task 3: Bimanual co-ordination (BMC)

Runs	Time required for positioning 6 pins OR 3 minutes	No of pins placed in 3 minutes	No of dropped objects
1	: :		
2	: :		
3	: :		

Appendix 9

Scoring sheets for laparoscopic suturing and knot quality:

European
 +theAcademy of
 Gynaecological
 Surgery

SUT+T1 EVALUATION

RESULT			
TIME:	:	:	max 15 min.
DOT:	0	1	2 3 4 5 6 7 8 9 10
CORRECT STITCH:	0	1	2 3 4 5
KNOT:	0 - 2	TRAUMA:	0 1 2

1) TIME

Time maximum - 15 minutes

2) DOT 0-1-2-3-4-5-6-7-8-9-10

To count dots through which the thread is passed correctly.

Dot may be counted when the stitch (thread) is entered in any point of the dot (when the thread is visually in contact with any part of the dot)
 Incorrect dot (not to be counted) is considered when the stitch is passed obviously out of the knot

3) CORRECT STITCH 0 – 5

The thread is passed correctly through **both dots**

4) TRAUMA

The damage of the suturing pad

0 = minimal, no damage | 1 = moderated damage | 2 = heavy damage

5) KNOT 0 – 1 - 2

Flat knot and two additional half knot

2 = knot is correct and tied | 0 = all the rest

Trauma

0: No damage, up to 4 needle puncture marks, no excavation, or exposed foam irrespective of the size of defect.

1: Between 5 and 8 needle puncture marks, defect in foam pad of less than 5mm or extent of trauma more than grade 0 but less than grade 2.

2: More than 8 needle puncture marks, Underlying foam exposed, defect in foam pad of 5mm or more, excavation and cavity formation.

Knot quality:

2: square knot, 3 throws and flat.

0: any of the above absent.

Knot quality should be assessed for each knot. Overall score for this section (knot quality) is the sum of all knots quality scores.

Appendix 10

Electromyography (EMG) protocol

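### The Tasks 2-3 primary score is in seconds for some trainees and in objects for others, so it gives no mean difference between specialties, and the protocol leaves open how the two kinds are compared

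*Protocol*

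**What the plan says.** Under Outcome measures, the primary outcome for Tasks 2 and 3 has three branches.

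- Finished in time: the team will "record the time taken in minutes and seconds to complete the tasks and use an average of this across 3 rounds".
- Not finished: "If the tasks are not completed within time (i.e. 3 minutes) then we will record the number of objects handled within 3 minutes", and this number is averaged over the three rounds.
- Mixed, spelled out as a trainee who "completes the task once in time (i.e. 3 minutes) but not on the other two runs". The score for such a trainee is in objects, whatever the time of the completed run: "then we will use the average number of handled objects over 3 runs and note the performance as mixed/inconsistent".

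The Task 2 and Task 3 procedures and the assessor instructions in Appendix 13 repeat the split: time if finished, otherwise a count at 3 minutes. The Appendix 8 sheets hold more than the outcome definition uses. For each run they have a time field ("Time required for inserting 6 cylinders OR 3 minutes" for Task 2, "Time required for positioning 6 pins OR 3 minutes" for Task 3) and a separate count field (for Task 2, "No of cylinders placed in 3 minutes").

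Objective 1 is to compare the two specialties at two training levels. Study Population sets 20 trainees per specialty, 10 per grade band.

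**The concern.** Which unit a trainee is scored in is decided by how well that trainee performs, and the units point in opposite directions: fewer seconds is better, more objects is better. No section converts one to the other or says how a trainee scored in seconds is set against one scored in objects.

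The choice of test can be left to an analysis plan. The per-trainee score cannot, because the protocol fixes it here. As fixed, it supports no difference in means, and it leaves three routes open: compare finishers' times, compare counts, or rank everyone. The first selects trainees on the outcome. The second puts every finisher at the ceiling of 6. If the route is chosen after the data are seen, the result for two of the four primary tasks could depend on that choice.

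**Working it through.** The protocol gives no power, SD, effect size or completion rate for these tasks, so there is no figure to reproduce. The first two steps need only the text. The third is an illustration on assumed inputs.

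**1. The rule by number of runs finished in time**

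| Runs finished | Score |
|---|---|
| 3 of 3 | mean seconds |
| 2 of 3 | not named; mean objects is the likely reading, because the non-completion sentence before it is general |
| 1 of 3 | mean objects, labelled mixed |
| 0 of 3 | mean objects |

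On the likely reading the scores can be fully ordered. A trainee scored in seconds placed 6 objects in every run. Anyone scored in objects missed at least one run, so averages at most (6 + 6 + 5)/3 = 5.67. All-finishers therefore rank above everyone else. They are ordered by time and the rest by mean objects.

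**2. What the mixed rule discards**

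| Runs | Mean objects (protocol) | Mean time, unfinished run = 180 s | Mean objects per minute |
|---|---|---|---|
| 120 s, 5, 5 | (6+5+5)/3 = 5.33 | (120+180+180)/3 = 160.0 s | (6/2 + 5/3 + 5/3)/3 = 2.11 |
| 179 s, 5, 5 | (6+5+5)/3 = 5.33 | (179+180+180)/3 = 179.7 s | (6/2.983 + 5/3 + 5/3)/3 = 1.78 |

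Both alternative scores separate the two trainees; the protocol's score does not.

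**3. Size, on assumed inputs**

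Assumptions: lognormal run times, log-SD 0.30 between and 0.20 within trainees, 180 s limit, 20 per specialty, two-sided 5%. Objects placed in an unfinished run are floor(6 × 180 / time), at most 5. The rank column is a Mann-Whitney test on the protocol's own scores, ordered as in step 1. The other columns are Welch t-tests. The rank, capped-time and objects-per-minute columns use 3,000 replicates; the finishers-only and counts columns use 6,000.

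| Group medians | Scored in objects, by group | Rank of protocol scores | Capped mean time | Objects per minute | Finishers' times only | Counts only |
|---|---|---|---|---|---|---|
| 60/80 s | 0.3/2.9% | 78.0% | 78.8% | 78.0% | 74.5% | 0.0% |
| 90/120 s | 5.9/24.0% | 76.0% | 78.0% | 76.7% | 55.6% | 22.4% |
| 110/150 s | 16.8/48.4% | 80.4% | 82.3% | 81.5% | 39.2% | 55.8% |
| 130/180 s | 31.7/69.5% | 84.0% | 83.4% | 85.3% | 25.1% | 75.6% |

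The largest loss from ranking is 78.0 − 76.0 = 2.0 points against capped time and 85.3 − 84.0 = 1.3 points against objects per minute. A second set of runs gave 76.8, 74.9, 80.3 and 84.3% for ranks against 77.2, 77.1, 82.8 and 84.2% for capped time. The largest loss there is 82.8 − 80.3 = 2.5 points.

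Other SDs (rank / capped time / objects per minute): at 0.40/0.30, 50.6/52.1/51.0% for 60/80 s and 58.8/58.0/58.8% for 130/180 s; at 0.20/0.15, 99.4/99.4/99.5% for 130/180 s. With no true difference the rank test rejects in 4.5 to 4.7%.

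Comparing finishers alone also shrinks the difference itself: 19.4 of 21.6 s, 19.1 of 32.2 s, 17.2 of 42.7 s and 14.9 of 53.8 s in the four cases.

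Trainees finishing two of three runs, the unnamed case, make up 0.2/2.2%, 4.2/13.2%, 10.0/19.3% and 15.7/19.3% of the groups.

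**The case against.** The strongest reply is that the score already orders all 40 trainees, so an ordinary rank test uses everyone without changing a word of the outcome rule, and naming that test belongs to an analysis plan that is not shown. Appendix 8 keeps time and count for every run, so nothing is lost for good. Nor is replacement free: capped time ties every trainee who finishes no run (up to 30.8% of a group in the slowest assumed case), whom the present rule separates by count.

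Most of this stands, and it rules out two stronger readings. A reader might infer that the trainees cannot be compared at all; step 1 shows that they can be ranked. A reader might also take the fall from about 74% to 25% power as the price of the switching rule. It is the price of comparing finishers' times alone, which the protocol does not propose. It would also go too far to say that a trainee with two of three runs has no score: the general non-completion sentence points to the object average, though it does not say so.

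What the reply does not answer is that the score yields no difference in seconds or in objects, that the ordering is the reader's inference rather than a stated rule, and that the inference depends on how two of three runs is read. It also depends on counting objects placed. The outcome paragraph counts objects handled, and a trainee could handle a sixth object without placing it.

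**Conclusion.** The point holds as a badly fixed outcome rule that should be corrected before the data are seen. From the text alone: the unit depends on performance, no mean difference between specialties can be formed across all 40 trainees, two of three runs is not named, and recorded speed is discarded for mixed trainees.

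If the scores are ranked, the statistical cost is small: at most about 2 to 3 points of power in the cases tried. The cost becomes large only if finishers' times or counts are compared alone, and the protocol rules out neither. All power figures rest on assumed lognormal times, medians and SDs. If nearly every trainee finishes every run, the choice between finishers' times and a single score hardly matters (74.5% against about 78% in the fastest case), although counts alone would then show almost nothing.

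**What to change.** Before the data are seen, state one score for all trainees on Tasks 2 and 3, built from the Appendix 8 fields. Either would do:

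- **Objects per minute:** for each run, objects correctly placed divided by the time used (at most 3 minutes), averaged over the three runs. This is less readable, but it separates trainees who finish no run: three runs of 5 give 5/3 = 1.67 per minute and three runs of 2 give 2/3 = 0.67.
- **Capped mean time:** mean time over the three runs with an unfinished run entered as 3 minutes. This stays in seconds, but both of those trainees score 180 s.

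If the present scores are kept, state that they are analysed by rank, with all-finishers (ordered by time) above all others (ordered by mean objects) and two of three runs counted as mixed.

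In every case keep the mixed/inconsistent note as a descriptive label and report the share of trainees completing each run.

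Two minor wording changes go with this. Replace handled by correctly placed in the outcome paragraph. Reconcile Table 1 with the task procedures and Appendix 13: for Task 2 it says "Ideal time for completion of task 2 is 3 minutes", with the same for Task 3, and it lists no count, whereas the other sections stop the run at 3 minutes and count objects.

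The cost is one outcome paragraph and two rows of Table 1. No new data are needed: a completed run is 6 objects, an unfinished run is 3 minutes, and the sheets already hold both fields.
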